## 13.2 Determination of Sample Size

Enrollment of 20 subjects with schizophrenia is estimated to provide approximately 80% power to detect a mean effect size of Cohen's *d*=0.5 with an error rate of alpha=0.10. Discontinued or withdrawn subjects and subjects for whom MMN is not available for all three study periods may be replaced. The sample size chosen of 20 completed subjects is considered to be sufficient to explore the changes in MMN between CVN058 and placebo as well as safety and tolerability of CVN058 in this population.

Sample size re-estimation may occur when MMN data from all 3 periods are available for 12 subjects, or when 20 subjects have been dosed and are expected to complete the study, whichever is sooner. To ensure adequate study power, sample size may be increased based on this re-estimation procedure. Further details will be included in the SAP.

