**Statistical Considerations:**

Observed values for the PD parameters (MMN and exploratory PD parameters) in each period will be summarized by treatment and compared to time matched assessments during placebo dosing using summary statistics. Comparison of post dose PD parameters to time matched placebo period timepoints will be analyzed using analysis of covariance (ANCOVA) with baseline value as a covariate and factors for sequence, subject nested within sequence, period, and treatment. Two-sided 95% confidence intervals will be constructed for the least squares mean differences between CVN058 and placebo in changes of PD parameters, comparing CVN058 and placebo at a time-matched post-dose time point.

Effect size will be calculated for comparisons of CVN058 to placebo using Cohen's  $d$  which expresses the difference between the means of 2 groups as a function of their pooled standard deviation.

Plasma PK concentrations and parameters of CVN058, and its metabolite if appropriate, will be listed and summarized by treatment using descriptive statistics. Exposure-response relationships for CVN058 will be explored graphically.

Adverse events (AEs) will be presented in listings, and treatment-emergent AEs (TEAEs) will be summarized by treatment. Individual results of vital signs will be listed and observed values and changes from Baseline in vital signs will be summarized by treatment.

Sample size re-estimation will occur after twelve (12) subjects have completed all study visits, or when 20 subjects have been dosed and are expected to complete the study, whichever is sooner. The sample size re-estimation will be performed using SAS® PROC POWER for Paired-Sample Means and specifications of power = 80%, alpha=0.10 and the unblinded group standard deviation values attained from the twelve study subjects.

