**Sample Size Justification:**

Enrollment of 20 subjects is estimated to provide >80% power to detect a median effect size of Cohen's  $d=0.5$ . Discontinued or withdrawn subjects and subjects for whom MMN is not available for all three study periods may be replaced. The sample size chosen of 20 completed subjects is expected to be sufficient to explore the changes in MMN between CVN058 and placebo as well as safety and tolerability of CVN058 in this population.

Sample size re-estimation may occur when MMN data from all 3 periods are available for 12 subjects, or when 20 subjects have been dosed and are expected to complete the study, whichever is sooner. Sample size may be increased up to a total of 40 subjects to ensure adequate study power to achieve its scientific objectives.

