### 13.1.6 Pharmacodynamic Analysis

Observed values for the PD parameters (MMN and exploratory PD parameters) will be summarized by treatment and compared to placebo using summary statistics. Comparison of post-dose PD parameters from a time-matched placebo period timepoint will be analyzed using analysis of covariance (ANCOVA) with factors for sequence, subject nested within sequence, period, and treatment. Two-sided 95% confidence intervals will be constructed for the LS mean of observed differences in PD parameters, comparing CVN058 and placebo at a time-matched post-dose time point.

Effect size will be calculated for comparisons of CVN058 to placebo using Cohen's *d* which expresses the difference between the means of 2 groups as a function of their pooled standard deviation.

Exposure-response relationships for CVN058 will be explored graphically.

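### The stated 80% power for 20 subjects gives neither the sides of alpha nor the SD behind d; on a paired-difference d it fits only a one-sided 10% test, while the reported two-sided 95% interval has about 56% power

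*Protocol*

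**What the plan says.** Section 13.2 of the current protocol (the version that introduces the unblinded interim) states: "Enrollment of 20 subjects with schizophrenia is estimated to provide approximately 80% power to detect a mean effect size". The effect is set at d=0.5, and the calculation is made "with an error rate of alpha=0.10". No sides are given, and no SD or within-subject correlation.

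The synopsis, under Sample Size Justification, says: "Enrollment of 20 subjects is estimated to provide >80% power to detect a median effect size of" d=0.5. It gives no alpha, claims more than 80% where Section 13.2 claims about 80%, and speaks of a median effect where Section 13.2 speaks of a mean.

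The synopsis, under Statistical Considerations, bases the re-estimation on "PROC POWER for Paired-Sample Means and specifications of power = 80%, alpha=0.10" and on group standard deviations from the first twelve subjects. Again it gives neither sides nor a correlation.

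For the final analysis, Section 13.1.6 says: "Two-sided 95% confidence intervals will be constructed for the LS mean of observed differences in PD parameters". The synopsis also calls for two-sided 95% intervals. Section 13.1.6 defines the reported Cohen's d with the pooled SD of the two groups. Section 13.1.2 adds an unblinded interim analysis on the first 12 subjects, with an O'Brien-Fleming boundary to control alpha and conditional power for futility.

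**The concern.** A power statement needs a test: an alpha, its sides, and an effect in the units that the test uses. Here the sides and the units are missing, and the interval chosen for reporting corresponds to a different error rate (two-sided 5%) from the one used for planning (10%, unsided). A reader who judges a dose by whether its 95% interval excludes zero will assume about 80% power and may have far less.

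The gap also affects decisions during the trial. The re-estimation may raise the sample size to 40, and its answer depends on the sides. The O'Brien-Fleming boundary and the conditional power also need a defined alpha with sides. Because the first 12 subjects' data are to be unblinded to the sponsor, a choice of sides made after that look could be informed by the data.

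**Working it through.** **Inputs.** N=20, d=0.5, alpha=0.10, power about 80% (Section 13.2). Paired-means test (synopsis; specified for the re-estimation and applied here to the planning figure). Two-sided 95% interval (Section 13.1.6). No allowance for dropout, because subjects without MMN in all three periods may be replaced. One dose-versus-placebo comparison, with no adjustment for two doses or for the interim.

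**Reading A: d is the mean paired difference divided by the SD of the paired differences.** This reading needs no unstated input beyond the sides. The paired t statistic is noncentral t with df = 20 − 1 = 19 and noncentrality 0.5 × √20 = 2.236. Power is the probability of exceeding the critical value (plus a negligible lower tail when two-sided).

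| Test | Critical t (df 19) | Power | Power, residual df 36 | Smallest N for 80% |
|---|---|---|---|---|
| One-sided 0.10 | 1.328 | 81.7% | 82.3% | 19 |
| Two-sided 0.10 | 1.729 | 69.5% | 70.9% | 27 |
| Two-sided 0.05 (95% interval) | 2.093 | 56.5% | 58.6% | 34 |

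The first row reproduces the protocol's figure; the other two do not. The 36 df are those of the crossover model in Section 13.1.6: 20 × 3 = 60 observations, less 1 for the mean, 5 for sequence, 14 for subject within sequence, 2 for period and 2 for treatment. At two-sided 5% with N=20, the paired d detectable with 80% power is about 0.66.

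**Reading B: d is per pooled group SD, as Section 13.1.6 defines it.** With equal variances, the SD of the paired difference is the group SD × √(2(1 − ρ)), so the paired effect is 0.5/√(2(1 − ρ)). At ρ=0.5 this is 0.5 and Reading A returns. The protocol gives no ρ, so the values below are assumptions.

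| Assumed ρ | Paired effect | One-sided 0.10 | Two-sided 0.10 | Two-sided 0.05 |
|---|---|---|---|---|
| 0.3 | 0.423 | 71.5% | 57.1% | 43.4% |
| 0.5 | 0.500 | 81.7% | 69.5% | 56.5% |
| 0.7 | 0.645 | 93.8% | 87.2% | 78.2% |

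On this reading, two-sided 10% reaches 80% power at ρ of about 0.62, and two-sided 5% at about 0.71.

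**Re-estimation.** At paired d=0.5, a one-sided 10% specification asks for 19 subjects (no increase over 20), and a two-sided 10% specification asks for 27 (an increase of 7). Group SDs alone do not determine the paired SD, so the correlation matters here too.

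**The case against.** The strongest reply is that nothing has been miscalculated. The primary objective is directional (improvement in MMN), a one-sided test fits it, and one-sided 10% gives 81.7%. That agrees with both the approximate 80% of Section 13.2 and the synopsis figure of more than 80%. This stands: the stated power can be reproduced, and the figure of more than 80% is not false on that reading.

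A reader might infer that only a one-sided test can deliver 80%, or that the trial simply has 56% power. Neither holds without a condition. Both assume d per SD of the paired difference; on the pooled-SD definition, a two-sided 10% test exceeds 80% once the correlation passes about 0.62. The 27-subject figure carries the same condition.

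A reader might also infer that the 95% interval is the plan's sole inference or its success criterion. The documents do not say so. Section 13.1.2 specifies an interim boundary, Section 13.2 names an error rate of 0.10, and no passage makes exclusion of zero by the 95% interval the criterion. A 95% interval reported beside a 10% test can be purely descriptive, but the protocol does not say that either.

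Sides and correlation in a power calculation are often left to the SAP, and this is an exploratory Phase 1 study that may grow to 40. At N=40 and paired d=0.5, two-sided 5% power is about 87%. But the increase is optional and is itself set at alpha=0.10. The protocol has already fixed the power, the alpha and the interval level, so a SAP cannot make them agree without contradicting one of them or adding the missing definition.

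**Conclusion.** The point holds as a mismatch between the stated power and the inference that the protocol fixes, caused by an undefined side and an undefined SD. It does not hold as an arithmetic error. With d per SD of the paired difference, power for 20 completers is 81.7%, 69.5% or 56.5% depending on the test, and the lowest of these belongs to the interval the protocol will report. With d per pooled group SD, the two-sided 5% figure is 43% to 78% for assumed correlations of 0.3 to 0.7.

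The consequence within the trial is that the unstated side can decide whether the re-estimation enlarges it: 19 versus 27 subjects at paired d=0.5. The synopsis and Section 13.2 also differ in wording (more than versus about 80%, median versus mean, alpha absent versus 0.10) and should agree.

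**What to change.** Before the unblinded interim analysis:

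1. In Section 13.2, the synopsis and the PROC POWER specification, state that alpha=0.10 is one-sided, if that was the intention, and that d=0.5 is the mean paired difference divided by the SD of paired differences. Alternatively, keep pooled-SD units and give the assumed within-subject correlation. Carry the same alpha and sides into the O'Brien-Fleming boundary and the conditional power.
2. Give the synopsis the same alpha, power and mean wording as Section 13.2.
3. Choose one of two routes. Either label the 95% interval descriptive and rest the decision on the one-sided 10% test, or keep the 95% interval as the basis for inference and restate power as about 56% on the paired-difference d (detectable paired d about 0.66 at 80%).
4. The pooled-SD Cohen's d in Section 13.1.6 may stay as a descriptive effect size, provided it is distinguished from the planning d.

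The cost is wording in the protocol and matching text in the SAP, with no new data or procedures. On the second route, a published power figure becomes less favourable.

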## 14.0 QUALITY CONTROL AND QUALITY ASSURANCE

### 14.1 Study-Site Monitoring Visits

Monitoring visits to the study site will be made periodically during the study to ensure that all aspects of the protocol are followed. Source documents will be reviewed for verification of data recorded on the eCRFs. Source documents are defined as original documents, data, and records. The investigator and institution guarantee access to source documents by the sponsor or its designee contract research organization (CRO) and by the IRB or IEC.

All aspects of the study and its documentation will be subject to review by the sponsor or designee (as long as blinding is not jeopardized), including but not limited to the Investigator's Binder, study medication, subject medical records, informed consent documentation, documentation of subject authorization to use personal health information (if separate from the informed consent forms), and review of eCRFs and associated source documents. It is important that the investigator and other study personnel are available during the monitoring visits and that sufficient time is devoted to the process.

### 14.2 Protocol Deviations

The investigator should not deviate from the protocol, except where necessary to eliminate an immediate hazard to study subjects. Should other unexpected circumstances arise that will require deviation from protocol-specified procedures, the investigator should consult with the sponsor or designee (and IRB or IEC, as required) to determine the appropriate course of action. There will be no exemptions (a prospectively approved deviation) from the inclusion or exclusion criteria.

The site should document all protocol deviations in the subject's source documents. In the event of a significant deviation, the site should notify the sponsor or its designee (and IRB or EC, as required). Significant deviations include, but are not limited to, those that involve fraud or misconduct, increase the health risk to the subject, or confound interpretation of primary study assessment. PK samples collected outside of the intervals (listed in [Table 14.a](#)), ECGs, vital signs, and RNA pharmacogenomic samples collected outside of the listed intervals are minor deviations and do not require the Protocol Deviation Form to be completed but must be documented in the subject's source documents. A Protocol Deviation eCRF should be completed by the site and signed by the sponsor or designee for any significant deviation from the protocol.

Every attempt will be made to collect each PK blood sample at the designated time point, and the actual time of each blood sample will be recorded on the source document and eCRF. [Table 14.a](#) defines the windows allowed for sample collections.

Protocol Deviations should be captured in the site source document for PK samples collected outside of the following intervals:

**Table 14.a Windows for Pharmacokinetic Blood Sample Collection**

Minutes	Nominal Sampling Time
no more than 15 minutes predose	Pre-dose (-0.25 hour)
±5	Postdose 1 hour
±15	Postdose 5 hours

### **14.3 Quality Assurance Audits and Regulatory Agency Inspections**

The study site also may be subject to quality assurance audits by the sponsor or designees. In this circumstance, the sponsor-designated auditor will contact the site in advance to arrange an auditing visit. The auditor may ask to visit the facilities where laboratory samples are collected, where the medication is stored and prepared, and any other facility used during the study. In addition, there is the possibility that this study may be inspected by regulatory agencies, including those of foreign governments (e.g., the Food and Drug Administration (FDA), the United Kingdom Medicines and Healthcare products Regulatory Agency, the Pharmaceuticals and Medical Devices Agency of Japan). If the study site is contacted for an inspection by a regulatory body, the sponsor should be notified immediately. The investigator and institution guarantee access for quality assurance auditors to all study documents as described in [Section 14.1](#).

## 15.0 ETHICAL ASPECTS OF THE STUDY

This study will be conducted with the highest respect for the individual participants (i.e., subjects) according to the protocol, the ethical principles that have their origin in the Declaration of Helsinki, and the ICH Harmonised Tripartite Guideline for GCP. Each investigator will conduct the study according to applicable local or regional regulatory requirements and align his or her conduct in accordance with the “Responsibilities of the Investigator” that are listed in [Appendix B](#). The principles of Helsinki are addressed through the protocol and through appendices containing requirements for informed consent and investigator responsibilities.

### 15.1 IRB and/or IEC Approval

IRBs and IECs must be constituted according to the applicable state and federal/local requirements of each participating region.

The sponsor or designee will supply relevant documents for submission to the respective IRB or IEC for the protocol’s review and approval. This protocol, the Investigator’s Brochure, a copy of the informed consent form, and, if applicable, subject recruitment materials and/or advertisements and other documents required by all applicable laws and regulations, must be submitted to a central or local IRB or IEC for approval. The IRB’s or IEC’s written approval of the protocol and subject informed consent must be obtained and submitted to the sponsor or designee before commencement of the study (i.e., before shipment of the sponsor-supplied drug or study specific Screening activity). The IRB or IEC approval must refer to the study by exact protocol title, number, and version date; identify versions of other documents (e.g., ICF) reviewed; and state the approval date. The sponsor will ship drug/notify site once the sponsor has confirmed the adequacy of site regulatory documentation and, when applicable, the sponsor has received permission from competent authority to begin the trial. Until the site receives drug/notification no protocol activities, including screening may occur.

Sites must adhere to all requirements stipulated by their respective IRB or IEC. This may include notification to the IRB or IEC regarding protocol amendments, updates to the informed consent form, recruitment materials intended for viewing by subjects, local safety reporting requirements, reports and updates regarding the ongoing review of the study at intervals specified by the respective IRB or IEC, and submission of the investigator’s final status report to IRB or IEC. All IRB and IEC approvals and relevant documentation for these items must be provided to the sponsor or its designee.

Subject incentives should not exert undue influence for participation. Payments to subjects must be approved by the IRB or IEC and sponsor.

### 15.2 Subject Information, Informed Consent, and Subject Authorization

Written consent documents will embody the elements of informed consent as described in the Declaration of Helsinki and the ICH Guidelines for GCP and will be in accordance with all applicable laws and regulations. The informed consent form, subject authorization form (if applicable), and subject information sheet (if applicable) describe the planned and permitted uses, transfers, and disclosures of the subject’s personal and personal health information for purposes of conducting the study. The informed consent form and the subject information sheet

(if applicable) further explain the nature of the study, its objectives, and potential risks and benefits, as well as the date informed consent is given. The informed consent form will detail the requirements of the participant and the fact that he or she is free to withdraw at any time without giving a reason and without prejudice to his or her further medical care.

The investigator is responsible for the preparation, content, and IRB or IEC approval of the informed consent form and if applicable, the subject authorization form. The informed consent form, subject authorization form (if applicable), and subject information sheet (if applicable) must be approved by both the IRB or IEC and the sponsor prior to use.

The informed consent form, subject authorization form (if applicable), and subject information sheet (if applicable) must be written in a language fully comprehensible to the prospective subject. It is the responsibility of the investigator to explain the detailed elements of the informed consent form, subject authorization form (if applicable), and subject information sheet (if applicable) to the subject. Information should be given in both oral and written form whenever possible and in the manner deemed appropriate by the IRB or IEC. In the event the subject is not capable of rendering adequate written informed consent, then the subject's legally acceptable representative may provide such consent for the subject in accordance with applicable laws and regulations.

The subject, or the subject's legally acceptable representative, must be given ample opportunity to: (1) inquire about details of the study and (2) decide whether or not to participate in the study. If the subject, or the subject's legally acceptable representative, determines he or she will participate in the study, then the informed consent form and subject authorization form (if applicable) must be signed and dated by the subject, or the subject's legally acceptable representative, at the time of consent and prior to the subject entering into the study. The subject or the subject's legally acceptable representative should be instructed to sign using their legal names, not nicknames, using blue or black ballpoint ink. The investigator must also sign and date the informed consent form and subject authorization (if applicable) at the time of consent and prior to subject entering into the study; however, the sponsor may allow a designee of the investigator to sign to the extent permitted by applicable law.

Once signed, the original informed consent form, subject authorization form (if applicable), and subject information sheet (if applicable) will be stored in the investigator's site file. The investigator must document the date the subject signs the informed consent in the subject's medical record. Copies of the signed informed consent form, the signed subject authorization form (if applicable), and subject information sheet (if applicable) shall be given to the subject.

All revised informed consent forms must be reviewed and signed by relevant subjects or the relevant subject's legally acceptable representative in the same manner as the original informed consent. The date the revised consent was obtained should be recorded in the subject's medical record, and the subject should receive a copy of the revised informed consent form.

Subjects who consented and provided a pharmacogenomic sample for DNA and RNA analysis can withdraw their consent and request disposal of a stored sample at any time prior to analysis. Notify sponsor of consent withdrawal.

### 15.3 Subject Confidentiality

The sponsor and designees affirm and uphold the principle of the subject's right to protection against invasion of privacy. Throughout this study, a subject's source data will only be linked to the sponsor's clinical study database or documentation via a unique identification number. As permitted by all applicable laws and regulations, limited subject attributes, such as sex, age, or date of birth, and subject initials may be used to verify the subject and accuracy of the subject's unique identification number.

To comply with ICH Guidelines for GCP and to verify compliance with this protocol, the sponsor requires the investigator to permit its monitor or designee's monitor, representatives from any regulatory authority (e.g., FDA, Medicines and Healthcare products Regulatory Agency, Pharmaceuticals and Medical Devices Agency), the sponsor's designated auditors, and the appropriate IRBs and IECs to review the subject's original medical records (source data or documents), including, but not limited to, laboratory test result reports, ECG reports, admission and discharge summaries for hospital admissions occurring during a subject's study participation, and autopsy reports. Access to a subject's original medical records requires the specific authorization of the subject as part of the informed consent process (see [Section 15.2](#)).

Copies of any subject source documents that are provided to the sponsor must have certain personally identifiable information removed (i.e., subject name, address, and other identifier fields not collected on the subject's eCRF).

